#### **4.3.2 Secondary endpoints**

- 1) Survival and Event free survival at 2 years and 3 years
- 2) Reduction in frequency of infections (evaluated at 1, 2 and 3 years after treatment based on clinical history and examination)
- 3) Long term immune reconstitution as assessed by sustained improvement in thymic function assessed by TRECS after 2 years post-gene therapy
- 4) Serum immunoglobulin levels for IgA, IgG and IgM and patients requiring immunoglobulin replacement therapy (recorded dichotomously).
- 5) Feasibility of the transduction procedure assessed by availability of greater than  $0.5 \times 10^6$  CD34+ cells/kg after transduction; undetectable RCL (determined retrospectively); and CD45+ cell viability after transduction equal to or greater than 50%, in accordance with the final product release criteria. These data will be reviewed and interpreted by the PI and the study team.

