function, including susceptibility to apoptosis and proliferative responses to mitogens and antigens (Cassani et al., 2008). Intravenous immunoglobulin treatment was discontinued in 5 children with evidence of antigen-specific antibodies to vaccinal antigens and pathogens. The progressive restoration of immune and metabolic functions led to significant improvement of patients' physical development and protection from severe infections, without adverse events related to gene therapy.

In a similar trial performed in London at our centre (Great Ormond Street Hospital for Children NHS Trust), using an alternative retroviral construct and a single dose melphalan conditioning regime (and latterly busulfan iv 4mg/kg), 7 patients have been treated (Gaspar et al., 2006) (and unpublished data, manuscript submitted). Three patients have shown very good immune recovery and in a fourth, gene transduced cells contributed to immune recovery although PEG-ADA was initially re-started and then stopped. Failure of gene therapy was seen in three patients, in one case as a result of a poor stem cell harvest and in two others due to low level stem cell transduction efficiency. In the two most successfully reconstituted patients, ADA expression was observed in different haematopoietic lineages, including red blood cells, leading to effective metabolic detoxification. The large majority of T cells and NK cells were gene corrected, while significant gene marking was also observed in granulocytes and monocytes. In these two individuals re-initiation of thymopoiesis after gene therapy was also noted.

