### **7.5.5 Testing prior to patient re-infusion**

Samples are collected during and at the end of the procedure for cell viability (trypan blue stain, 7AAD staining) and sterility (for bacteria, fungi and mycoplasma). Transduction efficiency (transgene PCR), and RCL testing will be performed after infusion of cells and recorded retrospectively.

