#### **8.8 Trial stopping criteria**

The trial will be stopped prematurely under the following circumstances:

1. Evidence of oncogenesis in any trial patient. The trial will only be re-started following agreement from both the MHRA and GTAC.

The events below will result in halting of the trial and will require a formal evaluation of the reasons for non-efficacy. The trial will only be re-started after discussion with and approval from the MHRA and GTAC:

1. Unsuccessful transduction of 3 consecutive patient CD34+ cells to specified criteria
2. No evidence of vector integration in 3 consecutive patients at 6 months post-treatment
3. 3 consecutive patients needing to re-start enzyme replacement therapy prior to 1 year post-gene therapy

*(From our experience of these studies, 3 consecutive patients would be seen as a number whereby this could not have happened by chance and is most likely related to processes or procedures)*

4. Emergence of new therapies for ADA-SCID, believed by the CI to be of greater benefit to this population of trial patients. The CI is in regular contact with other experts in the field of ADA-deficiency therefore is aware of new developments in the field. Regular reviews of the currently available treatment options for the subject population will be conducted by the PI throughout the trial.

Complete cessation of the trial would be made in consultation with the MHRA and GTAC.

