### **10.4 Description and justification of the trial treatment and dosage**

The EF1αS-ADA lentiviral vector is used to transduce autologous CD34+ cells *ex vivo*. These transduced cells are then infused into the patient. The cell/product dose will consist of at least  $0.5 \times 10^6$  CD34+ cells per kg of body weight transduced *ex vivo* with  $1 \times 10^8$  i.g./ml of lentiviral vector to achieve an average of 0.3-2 integrated copies per cell. A higher dose would be expected but given that there is a survival advantage to gene corrected cells, this lower level has been designated as final release threshold in this study. This is supported by evidence gained from our first retroviral ADA trial here at GOSH, where two patients reconstituted effectively, having received less than  $0.5 \times 10^6$  transduced CD34+ cells/kg (Gaspar et al., 2011).

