## 5.2 Secondary Endpoints

- Overall survival and event-free survival at 2 years and 3 years
- Frequency of infections (evaluated at 1, 2 and 3 years after treatment)
- TRECS after 2 years post-gene therapy
- Requirement for immunoglobulin replacement therapy (IgRT) and serum immunoglobulin levels for IgA, IgG and IgM.
- Feasibility of the transduction procedure assessed by availability of greater than  $0.5 \times 10^6$  CD34+ cells/kg after transduction; undetectable RCL (determined retrospectively); and CD45+ cell viability after transduction equal to or greater than 50%, in accordance with the final product release criteria. These data will be reviewed and interpreted by the PI and the study team and so will not be included in this SAP.

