### **8.2.14 IMP Administration**

Age at transplant in months will be calculated for the IMP treated subjects (on-study and CUP) as:

$$12 * (\text{date of transplant} - \text{date of birth}) / 365.25.$$

The duration of IMP infusion (in minutes) will be calculated as (end time – start time)/60.

The number (%) of subjects who received the IMP infusion and for whom the entire content of the bag was infused will be summarised along with the age at transplant, the duration of infusion, CD34+ cell dose, cell viability and volume.

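### The secondary endpoint on feasibility of transduction lists dose, RCL and viability but no measure of gene transfer, so its result does not depend on whether the cells were transduced

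*Protocol*

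**What the plan says.** Protocol 4.3.2 item 5 opens with "Feasibility of the transduction procedure assessed by availability of greater than" and then names a dose, 0.5 × 10^6 CD34+ cells/kg. Its other two parts are that no RCL is found, a result known only in retrospect, and that at least half of the CD45+ cells are viable. SAP 5.2 carries the same three parts, ending with "CD45+ cell viability after transduction equal to or greater than 50%, in accordance with the final product release criteria", and leaves the endpoint to the PI and study team, outside the SAP's analyses. It serves a named secondary objective (Protocol 4.2.2).

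The protocol deals with transduction of the product elsewhere:

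- Section 3.3.3 commits to evaluating transduction efficiency in ten subjects and hypothesises that the new vector will increase it.
- Section 7.5.4 sets cells aside for quality control that includes transduction efficiency. Section 7.5.5 adds: "Transduction efficiency (transgene PCR), and RCL testing will be performed after infusion of cells and recorded retrospectively".
- Table 3 (section 3.4.6), from a laboratory scale-up run, has a specification of more than 0.3 copies per cell. The two runs gave 1.34 and 0.96.
- Section 10.4 describes the vector concentration as chosen "to achieve an average of 0.3-2 integrated copies per cell".

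The IMP administration row of the schedule (Protocol Appendix 5, SAP 3) lists cell dose, viability and volume among the product items, but no copy number. SAP 8.2.14 has the infusion data "summarised along with the age at transplant, the duration of infusion", CD34+ dose, viability and volume, again without copy number.

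**The concern.** An endpoint named for transduction should be able to come out badly when transduction fails. This one cannot. Cells that were cultured, stayed viable and took up no vector satisfy all three parts, because the count is of CD34+ cells and not of gene-marked cells. The named secondary objective therefore cannot be answered from the endpoint as written.

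The practical loss is explanatory. If marking in patients is low, the first question is whether the product was poorly transduced or a well-transduced product failed to engraft. Product copy number answers that, and the plan neither lists it for the eCRF nor tabulates it. The centre has met this failure mode: in its earlier trial, Protocol 3.2.5 reports three failures among seven treated patients, "in one case as a result of a poor stem cell harvest and in two others due to low level stem cell transduction efficiency".

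**Working it through.** The plan gives no figure to reproduce. The check is whether the endpoint's result can change with vector copy number (VCN).

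**Inputs from the documents.** Dose above 0.5 × 10^6 CD34+ cells/kg, RCL undetectable and viability at least 50% (Protocol 4.3.2 item 5); specification above 0.3 copies per cell and observed values 0.96 and 1.34 (Protocol Table 3); aim 0.3–2 copies per cell (Protocol 10.4).

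**Assumptions.** For pass or fail, an example product with 5 × 10^6 CD34+ cells/kg, 90% viable, RCL undetectable. For the share of cells carrying vector, Poisson-distributed copies, so share = 1 − exp(−VCN). Neither comes from the documents.

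**Rule as written.** Feasible = (dose > 0.5 × 10^6/kg) and (RCL undetectable) and (viability ≥ 50%). VCN does not appear in it.

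Marked cells/kg at the dose threshold = 0.5 × 10^6 × (1 − exp(−VCN)). For example, at VCN 0.01: 0.5 × 10^6 × 0.00995 = 4,975. At VCN 0.3: 0.5 × 10^6 × 0.2592 = about 129,600.

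| VCN | Share marked | Marked cells/kg at 0.5 × 10^6/kg | As written | With > 0.3 added | With ≥ 0.3 added |
|---|---|---|---|---|---|
| 0 | 0 | 0 | pass | fail | fail |
| 0.01 | 1.0% | 4,975 | pass | fail | fail |
| 0.05 | 4.9% | 24,385 | pass | fail | fail |
| 0.1 | 9.5% | 47,581 | pass | fail | fail |
| 0.3 | 25.9% | 129,591 | pass | fail | pass |
| 0.96 | 61.7% | 308,554 | pass | pass | pass |
| 1.34 | 73.8% | 369,077 | pass | pass | pass |
| 2 | 86.5% | 432,332 | pass | pass | pass |

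The column for the rule as written is constant. Between VCN 0.01 and 0.3 the marked dose differs about 26-fold (129,591 / 4,975) and the endpoint does not move. The last two columns differ only at exactly 0.3, which is where Table 3 and section 10.4 disagree at the lower end.

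**Is late availability the reason for the omission?** No. Protocol 7.5.5 gives transgene PCR and RCL the same timing in one sentence, and RCL is in the endpoint, marked as retrospective.

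**Is the counted quantity consistent?** No. Protocol 4.1 and 8.4 apply the 0.5 × 10^6/kg figure to viable, transduced CD34+ cells. The endpoint applies it to CD34+ cells after the transduction step, with no marking requirement.

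**The case against.** **The release criteria may already contain copy number.** The endpoint is said to follow them, the full specification is not in the text available, and Table 3 and section 10.4 suggest that copy number belongs to the product definition. It may indeed sit in a retrospective specification; that cannot be settled here. But the endpoint lists its parts and copy number is not one, and a PCR result obtained after infusion cannot gate release of a fresh product.

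**Failed gene transfer would be seen anyway.** This stands in large part. Copy number in patient cells is a primary endpoint (Protocol 4.3.1, SAP 8.3.1.3), there is a 180-day transgene check (Protocol 4.1, 8.4), section 8.3 defines failure below 0.1% corrected cells, and halting criterion 2 in section 8.8 concerns absent vector integration. A reader might infer that the trial would be blind to failed transduction, or that it never measures it; the documents support neither. What is lost is the ability to separate poor transduction from poor engraftment.

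**The earlier failures are weak evidence.** This also stands. Two of three is a handful of patients given a different, retroviral vector, so it is no estimate of what this endpoint would miss. Nor is it established that the endpoint would catch a harvest failure: patients with too few cells for transduction are withdrawn before conditioning and replaced (Protocol 8.4).

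**Feasibility can mean that an adequate, viable, RCL-free product was made.** That is a defensible manufacturing endpoint, but it does not match the name or the stated objective.

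**A change now is late.** SAP 7.1 says that 10 subjects were recruited. This governs how the addition is labelled; it is no reason to leave the result unreported.

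**Conclusion.** The point holds as a gap in one descriptive secondary endpoint and its reporting. As listed, its parts give the same answer at every copy number from 0 to 2. That follows from the wording alone; only the marked-cell counts rest on the Poisson assumption. No primary result changes.

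It is tempting to extend the point to the halting rule, whose first criterion is "Unsuccessful transduction of 3 consecutive patient" products to specified criteria. A reader might infer that this rule is blind too. Protocol 8.8 does not say which criteria it means, and the copy-number specification in Table 3 fits at least as well as the feasibility parts do. The supportable statement is that the reference is undefined.

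**What to change.** 1. In Protocol 4.3.2 item 5 and SAP 5.2, add mean vector copies per cell in the infused product, by the transgene PCR already planned and determined retrospectively, as for RCL. Judge it against the lower specification the protocol already states (more than 0.3 copies per cell, Table 3), after reconciling that with the 0.3–2 aim in section 10.4. Do not treat 2 as a pass/fail upper limit unless the product specification says so.
2. Add product copy number to the IMP administration page of the eCRF, and add it with the number (%) meeting the specification to SAP 8.2.14. Label both the endpoint component and the table rows as late additions. Using a limit already in the protocol avoids a cut-off chosen from the data.
3. Reconcile the two descriptions of the 0.5 × 10^6/kg count: Protocol 4.1 and 8.4 against 4.3.2 item 5.
4. Ask the sponsor to state which criteria halting criterion 1 in Protocol 8.8 refers to. Their content is for the sponsor.

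Cost: no new assay or sample, one eCRF field and a few table rows. The protocol and SAP must be amended when product results may already be known in an open-label trial, and substantial protocol amendments need ethical and regulatory approval (Protocol 13). The reported feasibility rate may be lower.

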#### **4.3.3 Additional Endpoints**

- 1) T Cell V Beta Panel
- 2) Phytohaemagglutinin (PHA) stimulation Result
- 3) CD3 Stimulation
- 4) Integration Analysis Result
- 5) Bone Marrow Aspirate (if performed)
  - Morphology (Normal/ Abnormal).
  - Integration (Normal/ Abnormal).
  - Vector copy number in BM-MNC.

- 6) Tetanus Vaccination Response

## 5 Patient selection and recruitment

### 5.1 Patients treated with gene therapy (on trial)

Up to 10 treated patients will be recruited from the Immunology Unit at Great Ormond Street Hospital. Referrals for enrolment in the study will be accepted from centres worldwide. Individuals will be selected for inclusion on the basis of the following defined criteria:

#### 5.1.1 Inclusion criteria

1. Diagnosis of ADA-SCID confirmed by DNA sequencing OR by confirmed absence of <3% of ADA enzymatic activity in peripheral blood or (for neonates) in umbilical cord blood erythrocytes and/or leucocytes or in cultured foetal cells derived from either chorionic villus biopsy or amniocentesis, prior to institution of PEG-ADA replacement therapy
2. Patients who lack a fully HLA-matched family donor
3. Patients (male or female) < 5years of age OR  
  
Patients (male or female) ≥ 5years to 15rs of age who have preserved thymic function as evidenced by presence of >10 % naïve T cells (CD4+45RA+27+ cells)
4. Parental/guardian signed informed consent

#### 5.1.2 Exclusion criteria

1. Cytogenetic abnormalities on peripheral blood
2. Evidence of active malignant disease
3. Known sensitivity to busulfan
4. If applicable, confirmed pregnancy (to be tested in patients above 12 years old)

#### 5.1.3 Justification for enrolment criteria

In this study gene therapy will be offered in preference to a matched unrelated donor HSCT. To date over 30 patients have been treated with a gene therapy protocol involving cessation of PEG-ADA and non-myeloablative conditioning. All patients have survived the treatment and ~70% have been able to stop PEG-ADA. Furthermore, patients who have failed gene therapy have been able to restart PEG-ADA without any compromise to clinical or immunological well-being. In contrast, MUD transplants have a 67% survival (n=15). For these reasons, gene therapy offers a safer initial alternative and carries a high rate of success. If gene therapy fails,

patients can restart PEG-ADA or proceed to a transplant without compromising the success of the latter procedure.

Older patients have been shown to have a poorer response to gene therapy for ADA-SCID and also for SCID-X1 (Thrasher et al., 2005; Aiuti et al., 2009). This most probably relates to the low level of residual thymic function seen in older SCID patients as a result of diminished population of thymic tissue and also in the case of ADA-SCID ongoing thymic toxicity.

This also suggests that in the case of older patients (>5yrs of age), gene therapy will be of greatest benefit in those who have preserved thymic function as evidenced by the presence of > 10 % naïve t cells (CD4+45RA+27+ cells) and TRECs.

### **5.2 Patients treated with gene therapy (off trial): CUP group**

A group of patients were treated under the special compassionate group program (GOSH special license) either because the study was not yet open and patients needed urgent treatment, or because they were outside of the inclusion/exclusion criteria or received followed a different process (ie, received the Imp in two infusions). Patients followed however the same protocol steps and study visits. For this reason, CUP patients are included in the analysis, as described in the Statistical Analysis Plan (SAP)

### **5.3 Historical Control group: HSCT group**

A group of historical retrospective data has been collected from GOSH ADA-SCID patients treated with HSCT from year 2000. This group will be use as comparator data vs patients treated with gene therapy, to evaluate survival and event free survival, as described in the SAP. Below are the inclusion criteria for this population

#### **Inclusion criteria**

1. Diagnosis of ADA-SCID confirmed by DNA sequencing OR by confirmed absence of <3% of ADA enzymatic activity in peripheral blood or (for neonates) in umbilical cord blood erythrocytes and/or leucocytes or in cultured foetal cells derived from either chorionic villus biopsy or amniocentesis, prior to institution of PEG-ADA replacement therapy
2. Patients (male or female) between 0-18 years at time of treatment
3. Patient treated with allogeneic haematopoietic stem cell transplantation since 2000

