### **Papers 4 and 5: (Kaufman et al., 2005; Husain et al., 2007)**

These clinical reports document 2 children both of whom after 10 years of PEG-ADA therapy developed an EBV positive cerebral lymphoma and Burkitt's lymphoma respectively. Despite chemotherapy the first patient died 5 months after diagnosis of the tumour and the second patient responded to chemotherapy. In both patients there was poor recovery of cellular immunity on PEG-ADA which may have contributed to development of lymphoma. Other patients have also been reported who have developed malignancies after long term PEG-ADA administration.

**Figure 5:** Analysis of thymic output and T cell numbers in 5 HSCT treated patients and 8 PEG-ADA-treated ADA patients over time. The shaded areas represent the age related normal values in healthy children. A) Number of TREC5 B) Naïve T cell numbers as characterized by CD4+CD45RA+ expression C) Total T cell numbers. Figure from Serana et al., 2010.

These reports suggest that continued PEG-ADA treatment leads to demonstrable defects of T cell function and impaired thymic activity that may lead eventually to significant clinical infectious complications. It is also very probable that attempts to treat patients by either HSCT or stem cell gene therapy at this late stage will be unsuccessful or of limited efficacy due to reduced thymic function and increased infective burden (Thrasher et al., 2005).

Thus although PEG-ADA maybe an excellent short term measure to stabilise children with ADA-SCID, its prolonged use may be counter-productive.

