## Appendix 8: Details of the historical HSCT control group

### 1. Objective

Historical data from ADA-SCID patients who were treated with Hematopoietic Stem Cell Transplantation (HSCT) at GOSH during the period of 2000-2016 will be collected. HSCT is currently the standard of care for ADA-SCID patients. These data will be used as historical control group in a current on-going gene therapy study “Phase I/II, historical controlled, open-label, non-randomised, single-centre trial to assess the safety and efficacy of EF1αS-ADA lentiviral vector mediated gene modification of autologous CD34+ cells from ADA-deficient individuals”. The objective is to compare efficacy and safety of gene therapy versus HSCT to determine the optimal treatment.

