## **8.3.4 Sensitivity Analyses**

Protocol violations in this study will be reviewed prior to database lock in order to determine whether any major violations have occurred that could have influenced the outcome of the study. In the event that such violations have occurred, sensitivity analyses will be carried out in order to assess the impact of these violations on the efficacy results.

Sensitivity analyses will be carried out for:

- Overall and event free survival (descriptive statistics and Kaplan-Meier analyses)
- Lymphocyte subsets (descriptive statistics and plots)

- Measures of engraftment (descriptive statistics and plots)

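### The primary HSCT comparator is matched to the trial on donor availability only; age, malignancy and transplant year are not restricted, adjusted for or examined in any planned OS/EFS analysis.

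*Protocol*

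**What the plan says.** **Trial patients.** Protocol 5.1.1 takes "Patients who lack a fully HLA-matched family donor" who are under 5 years, or 5 to 15 years and "who have preserved thymic function as evidenced by presence of >10 % naïve T cells". Protocol 5.1.2 excludes cytogenetic abnormality, active malignancy, known busulfan sensitivity and confirmed pregnancy.

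**Controls.** Protocol 5.3 asks for confirmed ADA-SCID, "Patients (male or female) between 0-18 years at time of treatment" and "Patient treated with allogeneic haematopoietic stem cell transplantation since 2000". No exclusions are listed. Appendix 8 section 1 says the data come from patients treated "during the period of 2000-2016".

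**Primary comparator.** SAP 7.1 and 8.3 narrow this cohort to GOSH patients with no medically eligible HLA-matched sibling or family donor. The five secondary comparisons in SAP 8.3 vary only the donor group and whether CUP patients are included.

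**Analysis.** SAP 8.3.1.1 gives proportions, Kaplan-Meier curves and an unadjusted log-rank test; SAP 8.3.1.2 treats EFS the same way. Protocol 8.9.2 mentions proportional hazards models but names no covariate. SAP 8.3.4 starts from "Protocol violations in this study will be reviewed prior to database lock" and plans sensitivity analyses only if major violations are found.

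**Summaries.** SAP 8.2.15 lists age at transplant, donor type, conditioning type and prior ERT for controls. Transplant year is not listed.

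**The concern.** A child transplanted at 16, one aged 7 with poor thymic function, or one with active malignancy could not enter the trial but can sit in the primary control group. If such patients survive less often, their outcomes lower control OS and EFS, and the difference reads as benefit of gene therapy. Transplants spread over 2000-2016 add a second possible source of difference unrelated to the product.

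The Protocol itself treats timing as prognostic. Section 3.2.2.1, discussing prolonged PEG-ADA, rates the following as highly likely: "attempts to treat patients by either HSCT or stem cell gene therapy at this late stage will be unsuccessful or of limited efficacy". Section 3.2.2 adds that many patients who began ERT late had lung disease or other sequelae and were poor candidates for partially mismatched HSCT with conditioning. Mismatched transplants fall within the primary control group.

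The comparison carries weight: Appendix 8 aims to establish which treatment is best and wants the controls to support a marketing application. No planned output sets survival against age, malignancy or year.

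**Working it through.** The plan states no control sample size, event count, alpha or power, so there is no figure of its own to reproduce.

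**1. Criteria side by side**

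| Factor | Trial (Protocol 5.1) | Primary control group (Protocol 5.3, SAP 7.1) | Handled in OS/EFS analysis? |
|---|---|---|---|
| Matched family donor | none | none medically eligible | yes, by restriction |
| Age | under 5, or 5-15 with thymic function | 0-18 | no |
| Thymic function | over 10% naive T cells if 5 or older | no criterion | no |
| Active malignancy, cytogenetics | excluded | no criterion | no |
| Transplant year | not applicable | 2000-2016 | no |

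**2. What the donor restriction already achieves**

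Inputs are the survival figures in Protocol 3.2.1: MSD 86% (42 patients), MFD 81% (12), MUD 66% (15), MMUD 29% (7), haploidentical 43% (30). The numbers sum to 106, the stated total.

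- Matched related: (0.86×42 + 0.81×12)/54 = 45.84/54 = 84.9%.
- Other donors: (0.66×15 + 0.29×7 + 0.43×30)/52 = 24.83/52 = 47.8%.
- All: (45.84 + 24.83)/106 = 66.7%.

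In those data the donor restriction moves expected control survival by about 19 points against all donors (66.7 − 47.8) and 37 against matched donors (84.9 − 47.8). The factor with the largest documented effect is handled.

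**3. What is left**

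Let f be the share of controls outside the trial criteria and d their survival deficit. With no treatment effect, the apparent gain for gene therapy is f × d. Neither value is in the documents, so both are assumed:

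| f | d = 10 points | d = 30 points |
|---|---|---|
| 0 | 0 | 0 |
| 15% | 1.5 | 4.5 |
| 33% | 3.3 | 9.9 |

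The range is 0 to about 10 points. The 15% row is a proxy from Protocol 3.2.2: 70% of PEG-ADA patients began before age 1, and half of the remaining 30% began at 3 to 34 years. That is age at ERT start, not at transplant.

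**4. Effect on a nominal test**

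This is an illustration with a two-sided Fisher test at 0.05, which is not the SAP's test. It takes 10 treated patients, no treatment effect, and true survival of 67%, 80% or 90%. The chance of a significant result favouring gene therapy is:

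| Assumed controls | No bias | 10-point bias |
|---|---|---|
| 10 | 0.1-0.6% | 1.2-2.0% |
| 20 | 0-1.4% | 1.2-4.7% |
| 40 | 0-1.4% | 1.5-5.2% |

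The damage is mainly to the estimate.

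**5. Which data exist**

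Appendix 8 section 3 lists date of birth, date of treatment and malignant disease for controls. SAP 8.2.14 and 8.2.15 give age at transplant in both groups. Naive T-cell counts and cytogenetics are not listed for controls. SAP 8.3.1.1 expects some controls to have no recorded dates.

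**The case against.** The strongest defence has four parts.

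- **Donor type is already controlled.** A reader might infer that no analysis restricts controls towards trial eligibility. That is wrong: the primary comparator applies the trial's donor criterion, and Protocol 3.2.1 says donor source had a major impact on outcome. This part stands in full.
- **Imbalance in age would be visible.** SAP 8.2 tabulates age, age at diagnosis, time since diagnosis and medical history for both groups. This also stands, so it would be too strong to say that the output reveals nothing. But the tables do not relate these factors to outcome, and transplant year is missing from them.
- **Few controls may be ineligible.** Protocol section 6 says infants normally present in the first year, and children of 5 to 15 with thymic function remain eligible. The share outside may be near zero, which is why the range in the working starts at 0.
- **The comparison is descriptive, in a Phase I/II trial.** No alpha is set, and with up to 10 patients even 10 of 10 survivors gives an exact 95% interval of 69% to 100%. So this is not a broken error rate, and a shift of a few points could not be resolved. Yet Protocol 8.9.2 also speaks of statistical comparison, and Appendix 8 gives the contrast a decision-making purpose.

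Two stronger inferences are tempting. One is that age bias is demonstrated: section 3.2.2.1 states an expectation about patients after prolonged PEG-ADA, not HSCT survival by age, and the age statement in 5.1.3 concerns gene therapy. The other is that older transplants did worse: no section gives HSCT outcome by calendar period within 2000-2016.

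**Conclusion.** The point holds in this form. Beyond donor availability, the primary control group is not aligned with the trial on age, thymic function, malignancy or transplant year, and no planned OS or EFS analysis restricts, stratifies or adjusts for them. The estimate may be confounded.

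For age, the Protocol's own expectation suggests a bias in favour of gene therapy. For era, the direction is unknown. The 0 to 10 point range rests wholly on the assumed share (0-33%) and deficit (10-30 points). The documents do not support any single figure within it, or a claim that a spurious gain has been shown.

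This is a worthwhile, inexpensive improvement to the SAP. It does not invalidate the primary comparison.

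**What to change.** Leave the primary comparison as it is. Add to SAP 8.3.4, independent of any protocol violation, two pre-specified descriptive sensitivity analyses of OS and EFS:

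- **(a) Age.** Restrict both groups to patients under 5 years at transplant. Where records allow, also exclude controls whose malignancy is known to have been active at transplant.
- **(b) Era.** Present control outcomes by transplant year or period. Fix any cut-point before outcomes are examined, and report controls with unknown dates as such.

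Add transplant year to the control summaries in SAP 8.2.15. State openly that the naive T-cell and cytogenetic criteria cannot be applied, because neither is a listed control data item.

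The cost is SAP wording and a few tables from data already listed. The subsets will be small and their intervals wide, and analysis (a) also drops any trial patient aged 5 or over. The results should be read as a check on consistency, without formal testing.
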